### **8.3.2 *Missing Data Handling for 6MWD***

For the analysis of 6MWD, subjects may not have completed the treatment with study drug prior to the Week 48 visit for the following reasons: death, clinical worsening (per protocol definition), progressive disease (not meeting protocol definition of clinical worsening), AE unrelated to disease, withdrawal of consent by the subject, protocol deviation, loss to follow-up, termination of study by the sponsor, or withdrawal for other reasons. Every attempt must be made to perform all efficacy assessments immediately prior to premature termination of study drug or within 6 hours of the final study drug dose. In addition, subjects still receiving study drug may be too clinically ill to perform the 6MWT, resulting in missing data for that assessment.

In the analyses of 6MWD using nonparametric and parametric analysis of covariance methods, for subjects whose 6MWD measures at visits up to Week 48 are missing, the missing value will be imputed.

- For those subjects who have no 6MWD measurement due to death, too ill to perform 6MWT, or clinical worsening event, the 6MWD is set to the worst score of 0 meter.
- For missing data at visits prior to death or clinical worsening event, missing data will be imputed by the last observation carried forward (LOCF) approach.

- For all other reasons without 6MWD measurement, the LOCF approach will be used for imputation.

For missing 6MWD measures beyond Week 48, the missing data will not be imputed, and all analyses will be based on the observed cases.

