7.4 STUDY DRUG TERMINATION VISIT

Subjects will continue in the study until they experience clinical worsening, prematurely discontinue the study for any reason, or approximately 205 adjudicated clinical worsening events have occurred. If a subject remains ongoing with study treatment at the time when approximately 205 adjudicated clinical worsening events have occurred, the Study Drug Termination Visit should be scheduled as soon as possible. The following assessments will be conducted immediately after the decision is made to discontinue study drug (prior to down titration).

- Vital signs (following at least 5 minutes of rest)
- Physical examination
- Clinical worsening assessment
- WHO Functional Class for PAH
- AE assessment
- Drug accountability/compliance
- 12-lead ECG (following at least 5 minutes rest in the semi-recumbent position)
- Concomitant medications
- 6MWT/Borg dyspnea score (6MWT to be initiated 3 to 6 hours after last dose of study drug and following at least 5 minutes of rest; Borg dyspnea score to be conducted immediately following 6MWT)
- Urine pregnancy test (for WOCBP)
- Clinical laboratory tests/NT-proBNP

- Collection of blood sample for evaluation of blood biomarkers (optional)
- Collection of urine sample for evaluation of urine biomarkers (optional)
- Collection of blood sample for evaluation of pharmacogenomics (optional)

If the subject permanently discontinues study drug prior to Week 24 for any reason other than clinical worsening (e.g., AEs, addition of second PAH-approved oral therapy), the subject should immediately complete the study drug termination visit assessments and be encouraged to remain in the study and complete all visits up to and including Week 24. The Study Drug Termination Visit assessments should be conducted immediately after the decision is made to discontinue study drug (prior to down titration).

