10.2 SAMPLE SIZE

Approximately 205 adjudicated events will provide at least 90% power with a Type I error rate of 0.05 (two-sided hypothesis) to detect a difference in the time to clinical worsening between treatment groups, assuming exponential distributions and an underlying hazard ratio of 0.62. Assuming a placebo median event time of 32 months (which corresponds to an event rate of 23% at Month 12), this hazard ratio corresponds to a median time to event of 51 months for the UT-15C group, or an event rate of 15% at Month 12. If accrual of subjects is completed during the first three years and 10% of the subjects drop out by the end of the study, a total sample size of at least 610 subjects with a maximum of 850 subjects is expected to generate approximately 205 adjudicated events over the course of the study.

Based on the results of other PAH studies, (e.g., AMBITION [ambrisentan and tadalafil] and GRIPHON [selexipag]; Galiè, 2015; Sitbon, 2015) an interim analysis for efficacy is planned when 75% of the total adjudicated worsening events have occurred. In order to control the total alpha at a two-sided 0.05 level, the method of Lan and DeMets with O'Brien-Fleming-type alpha spending function will be used to calculate the boundaries for stopping the study for efficacy at the interim analysis [Lan and DeMets, 1983]. If the interim analysis is performed with 154 events, the boundary on the p-value scale will be 0.020 and 0.044 for the final analysis. Calculations will be performed in EAST version 6.4, Cytel Inc, using simulated power.

If enrollment continues beyond the interim efficacy analysis, final enrollment will be stopped when approximately 190 clinical worsening (morbidity or mortality) events have been reported by Investigators and reviewed by the Medical Monitor. Subjects will be followed until the occurrence of approximately 205 adjudicated clinical worsening events, at which time all remaining subjects will be transitioned to the open-label extension study. No more than 850 subjects will be enrolled.

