### 3 STUDY DESIGN

This is an international, multicenter, randomized, double-blind, placebo-controlled, event-driven study in subjects with PAH receiving background oral monotherapy. Subjects will be assessed during the Screening Period to determine eligibility for the study, which will be confirmed during the Baseline Visit prior to randomization. Once randomized, subjects will return for study visits every 4 weeks for the first 12 weeks, then every 12 weeks for the duration of the study. Subjects will continue in the study until they experience clinical worsening, as defined in the protocol, or they prematurely discontinue participation in the study for any reason other than protocol-specific clinical worsening.

If a subject meets the definition of clinical worsening during the study and receives only short-term (28 days or less) treatment with an infused or inhaled prostacyclin therapy for worsening PAH, they will be permitted to enter the open-label extension study (TDE-PH-311). If a subject prematurely discontinues the study for any reason other than clinical worsening, or receives long-term (29 days or more) treatment with an infused or inhaled prostacyclin therapy for worsening PAH, they will not be permitted to enter the open-label extension study.

An interim analysis for efficacy is planned when 75% (154) of the total (205) adjudicated clinical worsening events have occurred. All subjects actively participating in the study will be allowed to transition to the open-label extension study if the interim efficacy analysis is positive. If enrollment continues beyond the interim efficacy analysis, final enrollment will be stopped when approximately 190 clinical worsening (morbidity or mortality) events have been reported by Investigators and reviewed by the Medical Monitor. Subjects will be followed until the occurrence of approximately 205 adjudicated clinical worsening events, at which time all remaining subjects will be transitioned to the open-label extension study. No more than 850 subjects will be enrolled.

At each scheduled visit, subjects will undergo the following efficacy assessments: clinical worsening, exercise capacity (6MWD and Borg dyspnea score), and WHO FC.

Plasma samples will also be collected for measurement of NT-proBNP at Baseline, Week 12, Week 24, Continued Visit 1, and at every other continued visit thereafter.

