### ***8.3.3 Missing Data Handling for Other Efficacy Assessments***

Similar to 6MWD, analogous rules will be used for the main analyses of Borg dyspnea score and WHO FC. For subjects whose Borg dyspnea score or WHO FC at visits up to Week 48 or NT-proBNP values up to Week 36 are missing, the value will be imputed as follows:

Borg dyspnea score:

- For those subjects who withdrew early due to death, are too ill to perform 6MWT, or have no Borg dyspnea score due to clinical worsening event, the Borg dyspnea score is set to the worst score of 10.
- For missing data occurred at visits prior to death or clinical worsening event, missing data will be imputed by the LOCF approach.
- For all other withdrawals, the LOCF approach will be used for imputation.

For missing Borg dyspnea score at visits beyond Week 48, the missing data will not be imputed, and all analyses will be based on the observed case.

WHO FC:

- For those subjects who withdrew early due to death or have no WHO FC due to a clinical worsening event, the WHO FC is set to the worst value of class IV.
- For missing data occurred at visits prior to death or clinical worsening event, missing data will be imputed by the LOCF approach.
- For all other withdrawals, the LOCF approach will be used for imputation.

For missing WHO FC at visits beyond Week 48, the missing data will not be imputed, and all analyses will be based on the observed case.

NT-proBNP:

- For NT-proBNP, the missing value at visits up to Week 36 will be imputed using the LOCF approach.
- Subjects with missing Baseline NT-proBNP values, the Baseline measure will not be imputed, and these subjects will be excluded from the analyses of the NT-proBNP.

- Subjects with NT-proBNP values reported below the lower limit of quantification, half of the lower limit of quantification will be used for summary and analysis. For example, if the result is reported as '<2.4 pmol/L', a numeric value of  $2.4/2=1.2$  pmol/L will be used.

The missing values at visits beyond Week 36 will not be imputed and all analyses will be based on the observed cases.

Hemodynamics:

Missing values for hemodynamic parameters will not be imputed. The summary and analyses will be based on the observed cases.

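### The SAP does not separate a missed visit from one not yet due at study closure, so LOCF supplies Week 24, 36 and 48 values for late entrants

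*SAP*

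**What the plan says.** Protocol 10.2 lets enrolment run on after the interim: "final enrollment will be stopped when approximately 190 clinical worsening (morbidity or mortality) events have been reported by Investigators". Follow-up continues to about 205 adjudicated events, when all remaining subjects move to the extension study. For that closure, Protocol 7.4 says "the Study Drug Termination Visit should be scheduled as soon as possible", and the exit visit includes an on-treatment 6MWT and Borg score. There is one efficacy interim, at 154 events. SAP 3 adds: "All subjects actively participating in the study will be allowed to transition to the open-label extension study if the interim efficacy analysis is positive".

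SAP 8.3.2 lists sponsor termination of the study among the reasons why a subject may not complete treatment to Week 48. Its imputation rule has three parts: 0 m for death, too ill to walk or clinical worsening; LOCF for gaps before death or worsening; and "For all other reasons without 6MWD measurement, the LOCF approach will be used for imputation". SAP 8.3.3 repeats this for Borg and WHO FC: "For all other withdrawals, the LOCF approach will be used for imputation". SAP 8.6.2 specifies that the last valid on-treatment observation is carried.

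SAP 8.3 acknowledges that some subjects reach the end of an event-driven study without an event, but deals with this only for the time-to-event endpoint, by censoring. No rule covers a 6MWD, Borg or WHO FC visit that was not yet due at closure.

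**The concern.** Administrative closure truncates follow-up at a calendar date. For a subject randomised shortly before it, the Week 24 or Week 48 visit is not missing in the ordinary sense, because it was never scheduled to happen. Followed as written, the SAP still produces a value for it.

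For Week 24, the carried walk may come from Week 4, 8 or 12. Protocol Table 6-1 gives goal doses of 0.5-1.5 mg TID at Week 4 and 5.5-6.5 mg TID at Week 24, so a result labelled Week 24 would partly describe early titration. For Week 48, the carried value may come from Week 24 or 36.

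The analyses exposed are:
- the combined 6MWD/Borg test at Week 24 (SAP 10.2.3), which is formally tested and has no observed-case rerun;
- the supportive 6MWD rank ANCOVA and parametric ANCOVA, including Weeks 36 and 48;
- the exploratory Borg and WHO FC comparisons to Week 48;
- the additional LOCF analyses of NT-proBNP.

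The 6MWD MMRM (SAP 10.2.1) uses observed measures. The main NT-proBNP test (SAP 10.2.2) excludes subjects without a Week 24 value. Neither is touched.

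**Working it through.** **The plan's own figures.** Protocol 10.2 gives about 205 events, two-sided alpha 0.05 and at least 90% power, "assuming exponential distributions and an underlying hazard ratio of 0.62", with a placebo median of 32 months.
- Schoenfeld power: √(205/4) × |ln 0.62| − 1.960 = 7.159 × 0.478 − 1.960 = 1.46, or 92.8%. The stated floor is met.
- UT-15C median: 32/0.62 = 51.6 months (stated 51).
- Month 12 event rates: 1 − 0.5^(12/32) = 22.9% and 1 − 0.5^(12 × 0.62/32) = 14.9% (stated 23% and 15%).

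**When a visit can be observed.** SAP Table 8-1 opens the 6MWT Week 24 window after Study Day 127 and closes the Week 36 window at Day 295. First dose is on the day of randomisation and counts as Day 1. An exit walk from Day 128 therefore counts as an observed Week 24 value, and one from Day 296 as Week 48. A subject needs about 127/7 = 18.1 weeks on study for the first and 295/7 = 42.1 weeks for the second.

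**Deterministic model.** Uniform accrual; hazards ln2/32 and 0.62 × ln2/32 per month; enrolment closes at the cap or at 190 reported events, whichever is first; closure at 205 adjudicated events with no lag. Two inputs are assumed: the share of reported events upheld (100/90/80%) and a dropout hazard of 0.005 per month, which gives about 10% dropout in the 610 case. The counts are event-free subjects still in the study whose window had not opened.

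| Accrual | Upheld | Enrolment stop to closure, weeks | No possible Week 24 | No possible Week 48 |
|---|---|---|---|---|
| 610 in 36 months, capped | 100/90/80% | 37.6/41.7/47.2 | 0/0/0 | 15 (2.4%)/2 (0.3%)/0 |
| 730 pace | 100/90/80% | 14.3/18.7/32.8 | 16 (2.2%)/0/0 | 112 (15.4%)/92 (12.8%)/35 (5.1%) |
| 850 pace | 100/90/80% | 6.8/16.8/29.4 | 58 (7.2%)/7 (0.9%)/0 | 170 (20.9%)/117 (15.1%)/56 (7.6%) |
| Interim stop, 610 pace, capped | 100% | 3.4 | 54 (8.9%) | 135 (22.1%) |
| Interim stop, 850 pace | 100% | 0 | 94 (13.1%) | 206 (28.6%) |

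The gap column set against 18.1 and 42.1 weeks explains the pattern. Slower accrual (850 over 48 to 60 months, plan hazards) gives 0-5.3% and 0-17.0%.

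**Simulation.** This version spreads 10% dropout over 48 months (−ln 0.9/48 = 0.0022 per month), so events accrue a little faster. It also lets enrolment at the 610 pace continue past 610.
- Final analysis, Week 24: counting everyone under 24 weeks gives 57, 15 and 0 subjects at 0, 10 and 20% rejection. The Table 8-1 window reduces these to about 36 (5%), 3 (0.5%) and 0.
- Final analysis, Week 48, no rejection: 137 falls to about 118 of 688 (17%).
- Interim stop, Week 24: 88 falls to about 68 (11%).

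Over the 610 to 850 paces, the simulated ranges with the window applied are about 0-7% (Week 24) and 4-22% (Week 48) at the final analysis, and about 11-13% and 24-29% at an interim stop. With a cap of 610 over three years they are near 0% and about 1-6% at the final analysis.

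**Likelihood of an interim stop.** At the design hazard ratio and the 0.020 boundary: √(154/4) × 0.478 − 2.326 = 0.64, a 74% chance of crossing.

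**The case against.** The strongest reply is that little of this reaches formal inference. The 6MWD MMRM uses observed data and is extended to Week 48. The main NT-proBNP test is complete-case. SAP 10.2.1.1 already plans an observed-value rerun of the 6MWD rank ANCOVA. The combined test is reached only after two earlier successes, and the Week 36/48, Borg and WHO FC tests are declared exploratory. All of that stands, and it limits the importance of the point.

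Timing also helps the plan. Adjudication is periodic, and an interim stop needs a DMC review and a sponsor decision. The wording about exiting as soon as possible applies only to the 205-event closure. With an assumed two-month lag at the 610 pace, final Week 24 counts fall to about 7, 0 and 0, and the interim count to about 34, if no one enrols during the lag. If enrolment stays open, the relief is much smaller.

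A reader might infer four stronger things that the documents do not support.
- **Late entrants cannot reach Week 24.** This is conditional. With 610 subjects in three years essentially all can, and the protocol's estimated four-year duration would give the last entrant about 52 weeks. The 190 and 205 counts also differ in kind, reported against adjudicated, so every rejected event widens the gap.
- **The Week 24 effect shrinks by a known amount.** A figure of about 7% follows only from an assumed linear build-up to Week 24. No by-week effect is given for the TID regimen, and in one earlier BID study (Protocol 1.2.4) the estimate was +13 m at Week 12 and +11 m at Week 16.
- **The rule creates false positives.** Closure is a calendar event independent of arm, so the expected mechanism is mixing of earlier effects.
- **The first gatekeeping test is affected.** SAP 10.2.3 refers to the rank method as the key secondary methodology for 6MWD, but SAP 10.2.1 presents the MMRM first and 10.2.1.1 names it as the key secondary analysis. The wording should be aligned, but it does not show that LOCF enters that test.

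**Conclusion.** The concern holds as a gap in the imputation rule. Applied literally, SAP 8.3.2 and 8.3.3 assign a Week 24, 36 or 48 value to subjects for whom that visit was never due, including in the third formal test.

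At the final analysis this is a minor issue for Week 24 and a more substantial one for Week 48, though both nearly vanish if enrolment stops at 610 within three years. It is largest after an interim stop, which the design hazard ratio makes the likelier outcome.

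The sizes rest on the plan's hazards, uniform accrual, no lag to closure, and rejection rates that the documents do not give. Neither the magnitude nor the direction of any bias can be established from the documents. The change is worth making because the rule as written gives a mislabelled value and is easy to correct before unblinding.

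**What to change.** In SAP 8.3.2, 8.3.3 and 10.2.3, and for the additional LOCF NT-proBNP analyses, define one study-close date. For each imputed visit analysis, include all subjects randomised early enough for that visit's Table 8-1 window to have opened by that date: for 6MWD and Borg, beyond Study Day 127 for Week 24 and beyond Day 295 for Week 48. Include them whatever happened to them later, and do not impute a visit whose window had not opened.

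Select on randomisation date, not on who is still ongoing. Otherwise late entrants would stay in the set only if they died or worsened and were scored 0 m. Tie the cut-off to the analysis window, because a cut-off of 24 weeks plus the protocol visit window would discard genuine Week 24 walks. Keep the full-ITT LOCF version as a sensitivity analysis.

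No new data are needed. The costs are somewhat fewer subjects in these analyses, roughly the percentages above plus the few late entrants who had already had an event or dropped out, and a departure from the full ITT set for one formally tested endpoint. The change should therefore be documented before unblinding.

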### ***8.3.3 Missing Data Handling for Other Efficacy Assessments***

Similar to 6MWD, analogous rules will be used for the main analyses of Borg dyspnea score and WHO FC. For subjects whose Borg dyspnea score or WHO FC at visits up to Week 48 or NT-proBNP values up to Week 36 are missing, the value will be imputed as follows:

Borg dyspnea score:

- For those subjects who withdrew early due to death, are too ill to perform 6MWT, or have no Borg dyspnea score due to clinical worsening event, the Borg dyspnea score is set to the worst score of 10.
- For missing data occurred at visits prior to death or clinical worsening event, missing data will be imputed by the LOCF approach.
- For all other withdrawals, the LOCF approach will be used for imputation.

For missing Borg dyspnea score at visits beyond Week 48, the missing data will not be imputed, and all analyses will be based on the observed case.

WHO FC:

- For those subjects who withdrew early due to death or have no WHO FC due to a clinical worsening event, the WHO FC is set to the worst value of class IV.
- For missing data occurred at visits prior to death or clinical worsening event, missing data will be imputed by the LOCF approach.
- For all other withdrawals, the LOCF approach will be used for imputation.

For missing WHO FC at visits beyond Week 48, the missing data will not be imputed, and all analyses will be based on the observed case.

NT-proBNP:

- For NT-proBNP, the missing value at visits up to Week 36 will be imputed using the LOCF approach.
- Subjects with missing Baseline NT-proBNP values, the Baseline measure will not be imputed, and these subjects will be excluded from the analyses of the NT-proBNP.

- Subjects with NT-proBNP values reported below the lower limit of quantification, half of the lower limit of quantification will be used for summary and analysis. For example, if the result is reported as '<2.4 pmol/L', a numeric value of  $2.4/2=1.2$  pmol/L will be used.

The missing values at visits beyond Week 36 will not be imputed and all analyses will be based on the observed cases.

Hemodynamics:

Missing values for hemodynamic parameters will not be imputed. The summary and analyses will be based on the observed cases.

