1.2.4 Efficacy and Safety Data

UT-15C has previously been evaluated in three randomized, placebo-controlled Phase 3 studies (TDE-PH-301, TDE-PH-302, and TDE-PH-308). Additionally, subjects completing these studies have been provided long-term access to UT-15C in an open-label extension study (TDE-PH-304). To date, over 1000 PAH patients have been exposed to study drug (UT-15C or placebo) in the TDE-PH-301, TDE-PH-302, and TDE-PH-308 studies and over 890 patients have received UT-15C in the open-label extension study.

TDE-PH-301 was a 16-week, randomized, double-blind, placebo-controlled, international Phase 3 efficacy and safety study of treprostinil diethanolamine (UT-15C), in patients with PAH. Patients received UT-15C or placebo BID in combination with an ERA, a PDE5-I, or both. The primary endpoint was placebo-corrected change in 6MWD from Baseline to Week 16. Secondary endpoints included Borg dyspnea score, dyspnea-fatigue index, WHO Functional Class, and time to clinical worsening. Study drug dose was titrated up to a maximum of 16 mg BID based on clinical response and study drug tolerability.

Three-hundred fifty-four subjects were enrolled with 30% receiving an ERA alone, 25% a PDE5-I alone, and 45% both agents. The population was 81% female, predominantly WHO Functional Class III (76%), and had a mean baseline 6MWD of 346 m. PAH etiology included idiopathic or heritable PAH (66%), or PAH associated with CTD (26%), repaired congenital systemic-to-pulmonary shunt (7%), or HIV infection (1%). There were no remarkable demographic differences between treatment groups.

Twenty-two percent of subjects discontinued UT-15C therapy compared to 14% in the placebo group. The primary reason for discontinuation was AEs: 14% in the UT-15C group compared to 5% in placebo. There were three deaths in each of the treatment groups.

The Hodges-Lehmann (H-L) estimate of 6MWD placebo corrected median change from baseline at Week 16 was +11 m ($p=0.072$). The change in 6MWD was significant at Week 12 (+13 m, $p=0.015$). The lack of significance at Week 16 may be attributable to the number of subjects who did not provide an efficacy measure at Week 16 due to discontinuing from the study prematurely.

Secondary endpoints of the combined 6MWD and Borg dyspnea score and the dyspnea-fatigue index demonstrated statistically significant changes at Week 16 for UT-15C compared to Baseline ($p=0.013$ and 0.01 , respectively).

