TDE-PH-301 was initiated with subjects administered a 1 mg starting dose with dose increases in 1 mg increments. Additional tablet strengths of 0.5 and 0.25 mg were made available to subjects at sequentially later times in the study. A post-hoc analysis demonstrated

that during the course of the study those subjects with access to 0.25 mg tablets at randomization had a lower discontinuation rate due to AEs (0%, n=23) as well as a higher H-L estimate of 6MWD treatment effect (+28.5 m) at Week 16. Presumably titrating up the dose of study drug slowly with smaller increments may allow subjects to tolerate and thereby maintain therapy on UT-15C and achieve optimal dosing. In addition, those subjects that were able to titrate to doses between 1.25 and 3.25 mg BID and doses greater than or equal to 3.5 mg BID also demonstrated a more robust treatment effect of +18 and +34 m, respectively. Thus, premature discontinuations and inability to achieve doses greater than 1 mg BID during TDE-PH-301 appear to have muted the overall treatment effect detected by the study.

TDE-PH-302 was a 12-week, randomized (2:1 UT-15C to placebo), double-blind, placebo-controlled, international Phase 3 efficacy and safety study of UT-15C in patients with PAH not currently receiving approved background therapy. The primary endpoint was placebo corrected median change in 6MWD from Baseline to Week 12. Secondary endpoints included Borg dyspnea score, dyspnea-fatigue index, WHO Functional Class and time to clinical worsening. Study drug dose was titrated up to a maximum of 12 mg BID based on clinical response and study drug tolerability.

The study enrolled 349 subjects who were not receiving any approved PAH medication, with the population for primary analysis consisting of 228 subjects who had access to the 0.25 mg tablet strength at randomization. These subjects were administered UT-15C or placebo BID, with the doses titrated to effect over the course of the 12-week study. The majority of subjects were in WHO Functional Class II (33%) and class III (66%) of varied etiologies, including idiopathic or heritable PAH (75%), CVD associated PAH (19%), and PAH associated with HIV or other associated conditions (6%). The subjects' mean Baseline 6MWD was approximately 330 m.

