## 8.2 EXAMINATION OF SUBGROUPS

For the primary efficacy endpoint (time to adjudicated clinical worsening event), subgroup analyses will be performed. These subgroups will include:

- Background PAH therapy (PDE5-I or sGC stimulator only versus ERA only)
- Etiology of PAH (idiopathic/heritable, associated with collagen vascular disease, and other etiologies)

- Baseline walk categories ( $\leq 350$  m versus  $> 350$  m)
- Baseline WHO FC (class 1-2 versus class 3-4)
- Age group ( $< 65$  years versus  $\geq 65$  years)
- Sex (male versus female)
- Maximum dose achieved ( $< 9$  mg versus  $\geq 9$  mg total daily dose)
- Geographic region, categorized as North America (United States and Canada), Asia-Pacific (China, Taiwan, India, Australia, Singapore, South Korea), Europe (Germany, United Kingdom, Israel, Italy, Netherlands, Poland, France, Denmark, Greece, Austria, and Sweden), and South and Latin America (Mexico, Brazil, Chile, and Argentina)

Similarly, the subgroup analyses for subgroups listed above will also be performed for the key secondary endpoint of change from Baseline in 6MWD at Week 24.

No adjustment for multiplicity will be performed for these subgroup analyses.

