### **10.3.3 WHO FC**

WHO FC values (ie, class I, II, III, or IV) will be listed for all subjects at each assessment time point. Class I, II, III, or IV will be assigned values 1, 2, 3, 4 for the calculations. The shift from Baseline in WHO FC (categorized as Improved, No Change, and Deteriorated) for visits up to Week 48 will be compared between the 2 treatment groups using Fisher's exact test. The change from Baseline in WHO FC for visits up to Week 48 will be compared between the 2 treatment groups using the non-parametric Hodges-Lehmann estimator and Wilcoxon rank-sum test. Values for missing or excluded assessments up to Week 48 will be imputed. For those patients who withdrew early due to death or a clinical worsening event without WHO FC measurement at visits up to Week 48, the WHO FC is set to the worst class value of IV; for all other withdrawals without WHO FC measurement, the LOCF method is used for imputation.

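### WHO FC: imputing class IV after death lets a death from Baseline FC IV count as No Change, and ranks a death from Baseline FC III no worse than a survivor's one-class worsening

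*SAP*

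**What the plan says.** SAP 8.3.3 covers missing WHO FC at visits up to Week 48. For subjects who withdrew because of death, or who have no value because of a clinical worsening event, "the WHO FC is set to the worst value of class IV". SAP 10.3.3 repeats the rule ("the WHO FC is set to the worst class value of IV") and fixes the numeric scoring: "Class I, II, III, or IV will be assigned values 1, 2, 3, 4 for the calculations".

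Two comparisons follow in SAP 10.3.3, both on change from Baseline:

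- Fisher's exact test on the shift, "categorized as Improved, No Change, and Deteriorated".
- A comparison of the numeric change "using the non-parametric Hodges-Lehmann estimator and Wilcoxon rank-sum test".

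Protocol 10.3.2.3 plans the Wilcoxon test and has no rule for death. Neither document gives WHO FC a separate death category, a worst rank or a sensitivity analysis for this rule.

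FC IV at Baseline is possible. No criterion in Protocol 4.1 or 4.2 (repeated in SAP 15.1) restricts WHO FC, and the subgroup list in SAP 8.2 includes "Baseline WHO FC (class 1-2 versus class 3-4").

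**The concern.** The SAP calls IV the worst value, so the aim is plainly that death should count as the worst outcome. Class IV is, however, an ordinary living state (Protocol 15.2), and what is tested is the difference from Baseline. The penalty for dying therefore shrinks as the subject's Baseline class gets worse, and it vanishes at class IV. A Baseline FC IV subject can never be Deteriorated, even by dying.

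Two things are at stake. One is face validity: WHO FC is a named secondary objective, and its shift table could list a death as No Change. The other is the ordering used by the rank test, in which some deaths sit level with or above living subjects who got worse.

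**Working it through.** The documents state no figure on this point, so there is none to reproduce. The check is to apply the rule as written.

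**Inputs.** Scores 1 to 4 and the shift categories come from SAP 10.3.3. The imputed score of 4 after death comes from SAP 8.3.3 and 10.3.3.

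**Step 1: score each death.** Change = imputed score − Baseline score.

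| Baseline FC | Death scored 4 (SAP) | Shift category | Death scored 5 |
|---|---|---|---|
| I | 4 − 1 = +3 | Deteriorated | +4 |
| II | 4 − 2 = +2 | Deteriorated | +3 |
| III | 4 − 3 = +1 | Deteriorated | +2 |
| IV | 4 − 4 = 0 | No Change | +1 |

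**Step 2: compare with survivors.** A living II-to-III or III-to-IV change is +1, II-to-IV is +2 and I-to-IV is +3.

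- Death from IV (0) ties with stable survivors and ranks better than every survivor who worsened.
- Death from III (+1) ties with one-class worsening and ranks better than a living II-to-IV change.
- In the Fisher test a death from III is already in the worst category, so only the death from IV is misplaced there.
- A Baseline FC IV subject with a non-fatal clinical worsening event and no FC value also gets 4 − 4 = 0, No Change.

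**Step 3: would a fifth score repair it?** No. As the last column shows, a death from IV (+1) would still tie with one-class worsening and rank better than II-to-IV. A death from III (+2) would tie with II-to-IV. Only a common value above +3, the largest living change, puts every death last.

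**Step 4: how many deaths become No Change?** Expected number per arm = subjects per arm × proportion dead by the visit × FC IV share, if deaths follow the Baseline mix. The planned 610 to 850 subjects give 305 to 425 per arm. Deaths of 4% to 8% and FC IV shares of 2% and 5% are assumptions.

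- FC IV 2%: 305 × 0.04 × 0.02 = 0.24, up to 425 × 0.08 × 0.02 = 0.68.
- FC IV 5%: 305 × 0.04 × 0.05 = 0.61, up to 425 × 0.08 × 0.05 = 1.7.

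The number would be higher if deaths concentrate in FC IV.

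**Step 5: does it move the Wilcoxon test?** An illustrative simulation used 305 per arm, 20 v 8 deaths, the same survivor shifts in both arms and 300 replicates; the same data were scored both ways. All inputs are assumed. Survivor shifts were: I, 80% stable and 20% worse; II, 10% better, 80% stable and 10% worse; III, 25% better, 72% stable and 3% worse; IV, 50% better and 50% stable.

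| Baseline mix | Rejection, death = 4 | Rejection, common worst rank |
|---|---|---|
| II 33%, III 66%, I 1% | 0.100 | 0.103 |
| III 76%, II 22%, IV 2% | 0.120 | 0.123 |
| III 73%, II 25%, IV 2% | 0.123 | 0.133 |
| II 62%, III 34%, I 3%, IV 1% | 0.123 | 0.143 |

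The standard error of a rejection rate near 0.12 is √(0.12 × 0.88 / 300) = 0.019, and the median p-value fell by only 0.013 to 0.027. A second paired simulation, at an assumed 345 per arm, moved power by −0.2 to +1.9 percentage points when deaths favoured active treatment and by −0.8 to −1.3 points when deaths were equal. Worst-ranking death does not reliably add power.

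**The case against.** The strongest case for leaving the text alone has four parts.

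- **It is a consistent convention.** The SAP uses the worst value of each instrument: 0 m for 6MWD, 10 for Borg, IV for WHO FC. Change from any fixed bound depends on Baseline. This is true, but for 6MWD the bound cannot produce a zero change: entry requires at least 150 m, so a death is always a fall of at least 150 m. For WHO FC it can.
- **Little depends on it.** The WHO FC tests are exploratory and outside the fixed sequence (SAP 8.4). All-cause death is a primary-endpoint component, is analysed as time to death during the study and to study closure (SAP 10.1.1.3), and is summarised in safety (SAP 12.3). This stands in full and sets the grade.
- **The FC IV case is nearly empty.** TDE-PH-302 reports 33% FC II and 66% FC III, which leaves about 1% for I and IV together. This is fair, although that study is not this trial.
- **Ranking death below IV makes a composite that is no longer pure WHO FC.** This is also true, and is the reason to keep the present rule as a sensitivity analysis.

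A reader might infer that most deaths would score only +1 because most subjects are FC III. The documents do not support that for this trial, since neither gives its Baseline FC mix. The FC III shares of 76%, 66% and 73% belong to TDE-PH-301, 302 and 308. In 301 and 308, 45% and 40% of subjects took two background drugs, and in 302 none had approved background therapy; this trial requires monotherapy. If deaths followed the Baseline mix, the share scored +1 would be 66% to 76% under those studies' mixes, but 34% under the assumed FC II-majority mix above.

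**Conclusion.** The ordering defect is real and follows from the SAP text alone: a death from Baseline FC IV is No Change, and a death from Baseline FC III is a one-class change. The FC III part is confined to the Wilcoxon and Hodges-Lehmann results. The same No Change result arises for a Baseline FC IV subject with a clinical worsening event and no FC value.

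The size is small. Under the assumed shares, between about 0.2 and 1.7 deaths per arm would be listed as No Change, and the Wilcoxon result barely moves. A reader might also infer that the rule costs power or biases the comparison against UT-15C. That would need more deaths on placebo, which cannot be presumed, and the simulated differences are small and go in both directions. No power gain should be claimed. This is a minor improvement to an exploratory analysis, worth making because it carries out the SAP's own stated intent.

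**What to change.** In SAP 8.3.3 and 10.3.3, state that:

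1. A subject who has died by a visit is always classed Deteriorated in the shift analysis, whatever the Baseline class.
2. In the Wilcoxon test all deaths share one worst tied rank on the change scale, below every living change. Do not rely on coding death as 5.
3. A Baseline FC IV subject with a clinical worsening event and no FC measurement is also classed Deteriorated. The text should say what score that subject carries in the Wilcoxon test, so that the two analyses do not disagree unnoticed.
4. The current class IV rule is kept as a sensitivity analysis and for the Hodges-Lehmann estimate, which needs a numeric change.

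The cost is a few lines of text and code. No new data are needed, and alpha, sample size and the list of endpoints do not change. There are two downsides: the rank analysis becomes explicitly a composite of WHO FC and death, and its p-value and the Hodges-Lehmann estimate will rest on different scorings of death, which a table footnote should say.
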